### **Statistical analysis**

The data will be analyzed using Statistical Package for the Social Sciences (SPSS) for Windows 21.0 (IBM SPSS Statistics for Windows, Version 21.0. Armonk, NY: IBM Corp.) Software. They will be divided into groups by ensuring homogeneity according to gender. Patients' socio-demographic and clinical attributes, frequencies, percentage distribution, mean, and standard deviation will be provided.

Kolmogorov-Smirnov Test will be used to check the appropriateness of data to normal distribution. Independent two-sample t-test, one-way analysis of variance will be used for the relationships between the variables that fit the normal distribution, and the Mann Whitney U test will be used for the variables that do not fit the normal distribution. Pearson Chi-square significance test and Fisher Exact will be applied in the analysis of categorical data. All p values lower than 0.05 will be taken as significant in all results ( $p < 0.05$ ).

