#### Intervention and Assessment

The appropriateness of patients who have received mechanical ventilator support using an ETT in the ICUs will be evaluated based on the inclusion and exclusion criteria. The patients who have been included in the study will be evaluated in terms of age, gender, height, weight, body mass index, medical diagnosis, chronic diseases, consciousness, presence of nasogastric (NG) tube, position, the reason for intubation, type of nutrition, drugs used (antibiotics, stress ulcer prophylaxis and sedative agents), Ramsay Sedation Score (RSS), transport and transfusion status, ventilator, respiration and hemodynamic values.

The cuff pressure of the patients in all groups will be controlled every eight hours. Smart cuff manager will be attached to the patients in study group 2. Samples will be taken from the

patients through open aspiration. The first deep tracheal secretion sample to be used to determine pepsin I level will be taken four hours after intubation. A sampling of the tracheal secretion samples to be used in the determination of pepsin II level will be initiated from the 5th hour after intubation and collected by the 24th hour of the intubation. A sampling of the tracheal secretion samples to be used in determination of pepsin III levels will be initiated from the 25th hour after intubation and collected by the 48th hour of the intubation or the patient is discharged or exitus.

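### The groups are meant to be alike on gender, but no listed test uses gender; adding it would be a minor, optional gain in precision

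*Combined protocol and SAP*

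**What the plan says.** On forming the groups, the Statistical analysis section states: "They will be divided into groups by ensuring homogeneity according to gender". This is the only mention of balancing on gender. No mechanism is given there, in Study design or in Study population.

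The tests follow in the same section:

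- Normally distributed variables: "Independent two-sample t-test, one-way analysis of variance will be used for the relationships between the variables that fit the normal distribution".
- Other variables: "the Mann Whitney U test will be used for the variables that do not fit the normal distribution".
- Categorical variables: "Pearson Chi-square significance test and Fisher Exact will be applied in the analysis of categorical data".
- Threshold: "All p values lower than 0.05 will be taken as significant in all results". Sidedness is not stated.

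No analysis of covariance, two-way ANOVA, regression or stratified test appears anywhere in the document. Gender is among the baseline items in Intervention and Assessment, where patients "will be evaluated in terms of age, gender, height, weight, body mass index" and more. The same section defines three pepsin measurements (I, II and III). The analysis section links no test to any of them.

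**The concern.** A factor used to make groups alike normally reappears in the analysis. If balance is enforced, chance differences in gender no longer add to the variability of the group difference. An unadjusted test still counts gender-related variation in its error term, so its standard error is too large whenever gender predicts the outcome. P-values are then too high and intervals too wide.

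A chi-square or Fisher test of gender between groups would be a balance check only. It would not adjust the pepsin comparison.

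What is at stake is some power and some interval width. Because gender is already recorded, recovering them needs no new data.

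**Working it through.** **Inputs from the plan (Study population):** d=0.5, alpha 0.05, power 0.80, 51 per group, raised to 56 for losses.

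**Assumption:** the share of within-group pepsin variance explained by gender, R². The documents give no value, so 1%, 5%, 10% and 20% are shown.

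**1. The plan's own figure.** A one-sided two-group comparison needs 2(1.645+0.842)²/0.5² = 49.5, so 50 per group by the normal approximation. The exact t-test gives 50.15, rounded up to 51, which matches. The two-sided t-test gives 63.8, so 64. The 51 therefore fits an unadjusted one-sided t-test with no gender term. Sidedness is a separate matter. Two-sided tests are used below; two-sided power at 51 per group is 0.706.

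**2. Why the unadjusted test can be conservative.** Set the total within-group variance to 1, with R² due to gender and 1−R² residual. With exact balance, gender cancels from the difference in means, whose true variance is 2(1−R²)/n. The t-test estimates about 2/n. Real size is therefore about 2{1−Φ(1.96/√(1−R²))}. For R²=0.10, 1.96/√0.90 = 2.066, which gives 0.0388.

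Size of a nominal 0.05 test, simulated with 56 per group:

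| R² | Formula | t-test, exact balance | Gender-adjusted, exact balance | t-test, no balancing | Gender-adjusted, no balancing |
|---|---|---|---|---|---|
| 1% | 0.0489 | 0.0490 | 0.0502 | 0.0497 | 0.0499 |
| 5% | 0.0443 | 0.0446 | 0.0501 | 0.0503 | 0.0498 |
| 10% | 0.0388 | 0.0391 | 0.0499 | 0.0492 | 0.0493 |
| 20% | 0.0284 | 0.0283 | 0.0496 | 0.0501 | 0.0501 |

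A 28/28 gender split was used for exact balance. A 34/22 split in each group gives 0.0449, 0.0387 and 0.0291 unadjusted at 5%, 10% and 20%, so an even split is not needed. Under exact balance the same pattern holds for Mann-Whitney U (0.047, 0.045, 0.039, 0.028) and three-arm ANOVA (0.0489, 0.0421, 0.0358, 0.0240). In no setting does size rise materially above 0.05.

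**3. Power at d=0.5, two-sided t-test, 52 per group** (51 cannot be split evenly by gender), unadjusted to adjusted:

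| R² | Exact balance | Gain (points) | No balancing | Gain (points) |
|---|---|---|---|---|
| 0 | 0.7129 to 0.7129 | 0.0 | 0.7127 to 0.7083 | −0.4 |
| 1% | 0.7142 to 0.7175 | 0.3 | 0.7140 to 0.7149 | 0.1 |
| 5% | 0.7189 to 0.7368 | 1.8 | 0.7131 to 0.7312 | 1.8 |
| 10% | 0.7241 to 0.7587 | 3.5 | 0.7134 to 0.7544 | 4.1 |
| 20% | 0.7327 to 0.8046 | 7.2 | 0.7145 to 0.8032 | 8.9 |

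Under exact balance the adjusted interval is 0.995, 0.974, 0.948 and 0.893 times as wide, for R² from 1% to 20%.

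**4. Rank test.** Mann-Whitney U against a gender-stratified rank test (van Elteren), exact balance, 52 per group, R² = 0, 1%, 5%, 10%, 20%: 0.692 to 0.686, 0.691 to 0.691, 0.696 to 0.710, 0.699 to 0.733, 0.706 to 0.781. Gains are −0.6, 0.0, 1.4, 3.4 and 7.5 points. These figures agree with a re-run under normal errors. They are only a guide to the skewed data for which the plan would use ranks.

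**5. Three-arm ANOVA** with assumed means 0, 0.25 and 0.5 SD, exact balance, 52 per group, same R² values: 0.612 to 0.612, 0.610 to 0.615, 0.609 to 0.634, 0.607 to 0.662, 0.605 to 0.717.

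**The case against.** The strongest reply is that this is a refinement and not an error. Nothing in the documents says gender predicts pepsin, and the sizeable gains come only from the assumed 10% and 20%. At 1% the gain is 0.3 points or less, and the stratified rank test gains nothing. This stands, and it is why the point is minor.

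A second reply is that gender may not be a design factor at all. The sentence sits in the analysis section and could describe an allocation constraint, or only a similarity that is hoped for or checked. This also stands. If gender did not constrain allocation, the design gives no reason to prefer it to other recorded baseline items. The calculation survives, because the gains from adjustment are similar with exact balance and with none.

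Third, the van Elteren test compares two groups only, and its availability in the named software is not shown. This stands, and the fix does not depend on it.

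A reader might go further and infer that the unadjusted tests are invalid, biased or prone to false positives. The documents do not support that: in every case checked, size is at or below about 0.05.

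**Conclusion.** The point holds as a minor one. The plan states an aim of gender homogeneity and lists no test that uses gender. That the pepsin comparisons are unadjusted is an inference from the general list of tests.

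The consequence is confined to precision: roughly 0 to 2 points of two-sided t-test power if gender explains up to 5% of pepsin variance, and about 3.5 and 7 points at 10% and 20% under exact balance. All of these shares are assumptions, and the true benefit may be close to zero. It would be too strong to read the homogeneity sentence as proof of stratified allocation, or as evidence that gender matters for pepsin. The text establishes neither.

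**What to change.** Optional, for precision:

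- Prespecify a linear model with group (three levels) and gender for the between-group pepsin comparisons. Fix one scale in advance, for example log pepsin, and state a rule for zero or undetectable values.
- If a rank analysis is needed, prespecify a gender-adjusted version that covers both the three-arm and the pairwise comparisons, such as the same model fitted to ranked pepsin. Alternatively, keep Mann-Whitney U for the pairwise comparisons and accept the small loss.
- As a clarification only, state how gender homogeneity is achieved (for example by stratification, matching or minimisation).

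Cost: analysis wording and one degree of freedom, with no new data and no extra patients. SPSS fits the linear model with its general linear model procedure. If gender explains nothing, the price is up to about 0.4 points of power for the linear model, or 0.6 points for a stratified rank test.

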#### Study design

This is a single-blind randomized controlled trial that compares finger palpation of the pilot balloon, intermittent and continuous ETT cuff pressure used to prevent microaspiration of gastric content for ICU patients.

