#### Study population

The population of the study consists of the patients hospitalized in the Internal Medicine, Neurology, Neurosurgery, General Surgery, Anesthesia, Isolation and Diseases ICU of University Hospital. Inclusion criteria for the sampling of the study are as follows: being 18 years and above, voluntariness of the patients or their relatives, and having a need of mechanical ventilator support with an ETT for 48 hours. The criteria of exclusion from the sample are as follows: having contraindication of semi-sitting position, having a contraindication to enteral nutrition, patients who have spent more than 48 hours on a mechanical ventilator at the initial assessment, having tracheostomy, gastroesophageal reflux disease (GERD), aspiration pneumonia or any suspicion of it, and nasal ETT intubation. Power analysis was done to determine the number of patients to be distributed to Group 1, Group 2, and the control groups. The power analysis was done using GPower 1.3.9.2 software. Thus, the significance level was  $\alpha=0.05$  (%5), the effect size was  $d=0.5$ , and the number of patients in each group was 51 for the power at  $1-\beta=0.80$ . Missing, bad or lost data (in case patients were exitus) were considered and the number of patients was designed to be 56 for each group

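### Six or seven ICUs recruit, but gender is the only balancing factor named and no planned test uses ICU: a cheap gain in precision is left unused

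*Combined protocol and SAP*

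**What the plan says.** The Study population section draws patients from "Internal Medicine, Neurology, Neurosurgery, General Surgery, Anesthesia, Isolation and Diseases ICU of University Hospital". That is seven units, or six if the last two names belong to one unit.

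The Study design section describes a randomised, single-blind trial that "compares finger palpation of the pilot balloon, intermittent and continuous ETT cuff pressure". It gives no method of sequence generation, blocking or concealment. The only statement about balance is in the Statistical analysis section: "They will be divided into groups by ensuring homogeneity according to gender".

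The planned tests are all unadjusted:
- Normally distributed outcomes: "Independent two-sample t-test, one-way analysis of variance will be used for the relationships between the variables that fit the normal distribution"
- Skewed outcomes go to Mann-Whitney U, again with no covariate.
- Proportions and counts: "Pearson Chi-square significance test and Fisher Exact will be applied in the analysis of categorical data"

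The Intervention and Assessment section lists many baseline variables, among them diagnosis, reason for intubation, nutrition and sedation. ICU is not on that list.

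**The concern.** Several of the recorded baseline variables could plausibly track the type of unit, and some could plausibly relate to pepsin. ICU is a single, easily recorded proxy for them. If the plan balances one factor, it gives no reason to prefer gender to ICU.

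When ICU is ignored in both allocation and analysis, whatever between-unit variation exists stays in the error term. The ICU mix of the arms is then left to chance, with no correction. What is at stake is the precision of the pepsin comparison, and how readily a reader accepts the result if the arms turn out visibly uneven by unit.

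**Working it through.** **Inputs from the documents.** Three arms; α = 0.05, sidedness not stated; power 0.80; d = 0.5; 51 evaluable and 56 planned per arm, so 168 in total (Study population).

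**Assumed, because the documents are silent.** ICU sizes, and the share ρ of pepsin variance that ICU explains, taken as 5% to 20%. The true share could be near zero.

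**1. The plan's own figure.** For a two-sample t-test with 51 per arm, the noncentrality is d·√(n/2) = 0.5·√(51/2) = 2.525 on 100 degrees of freedom.
- One-sided at 0.05: power is 80.6%, and 51 is the smallest n that reaches 80%. The figure is reproduced.
- Two-sided at 0.05: power at 51 is 70.6%, and 64 per arm would be needed.

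Both versions are carried forward because the plan does not state sidedness.

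**2. How uneven the ICU mix can be.** Assume 7 ICUs of 168/7 = 24 patients each, and an allocation that ignores ICU. One arm's count in one ICU is hypergeometric with mean 24 × 56/168 = 8. Its variance is 24 × (1/3) × (2/3) × (144/167) = 4.60, so the SD is 2.14; the 95% range is 4 to 12. In 20,000 simulated allocations, at least one ICU had a gap of 6 or more patients between its largest and smallest arm in 89% of trials, and of 8 or more in 53%. These figures describe the worst of seven units, so they show that visible imbalance is likely. They do not measure its effect on pepsin.

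**3. The effect on pepsin and on power.** With the outcome SD set to 1, the ICU-driven chance difference between two arms has SD √(2ρ/n), so its 95% range is ±1.96·√(2ρ/51). Adjusting for ICU cuts the residual variance to 1 − ρ, so the effective d becomes 0.5/√(1 − ρ). The few degrees of freedom spent on ICU are ignored here.

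| ρ (assumed) | ICU-driven difference, 95% range (SD) | Effective d after adjustment | Power, one-sided | Power, two-sided | Equivalent sample, 1/(1 − ρ) |
|---|---|---|---|---|---|
| 0 | 0 | 0.500 | 80.6% | 70.6% | 1.00 |
| 5% | ±0.09 | 0.513 | 82.3% | 72.8% | 1.05 |
| 10% | ±0.12 | 0.527 | 84.1% | 75.0% | 1.11 |
| 20% | ±0.17 | 0.559 | 87.7% | 79.8% | 1.25 |

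Against the target of 0.5 SD, the chance difference runs from 0.087/0.5 = 17% to 0.174/0.5 = 35% of the target.

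**4. Type I error.** In 20,000 simulated t-tests with 56 per arm and 7 ICUs, the unadjusted test after simple randomisation rejected in 5.0%, 4.8% and 4.7% of null trials for ρ of 10%, 20% and 30%. The level holds. If patients were balanced by ICU but ICU were left out of the test, the rates fell to 3.9%, 2.8% and 1.7%. Allocation and analysis therefore need to change together.

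**The case against.** The strongest reply is that randomisation already deals with this. The error term of an unadjusted test includes the chance imbalance between units, so chance imbalance and extra residual variance are one loss of precision, not two separate harms. This stands, and step 4 confirms it. A reader might infer that the pepsin comparison is biased or that false positives are inflated; the documents do not support that for a trial described as randomised. Whether the allocation method is itself sound cannot be judged, because none is described. That is arguably the larger gap.

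A reader might also infer that the units are known to differ in case mix, or that different staff palpate the balloon and take the samples in each unit. The documents say neither. They record sedation, consciousness and similar variables without saying that these vary by unit, and they do not say who performs the tasks; one team could cover the whole hospital. The exclusion criteria also narrow the case mix. The case for using ICU therefore rests on plausibility.

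Two further replies stand in part. The gender sentence sits among the analysis methods and its literal subject is the data, so reading it as an allocation rule is reasonable but remains an interpretation. And adding a factor is not automatic: the plan lists separate tests with no model, and Mann-Whitney U takes no ICU term. The fix has to name a replacement.

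**Conclusion.** The point holds as a cheap improvement. It is not a validity flaw. ICU is absent from both allocation and analysis, and at 56 per arm an uneven ICU mix is likely by chance.

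The benefit of using ICU depends on an assumed variance share. At 5% the power gain is about 2 percentage points (80.6% to 82.3% one-sided, 70.6% to 72.8% two-sided). At 20% it is 7 points one-sided and 9 points two-sided, and near zero share there is no gain. The two-sided case matters more, since 51 per arm then starts from 70.6%. The 89% chance of a gap of 6 or more in some unit should not be read as an 89% chance of a misleading result.

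**What to change.** - **Record ICU.** Add it to the baseline variables in the Intervention and Assessment section.
- **Allocation.** State the randomisation method. Either stratify the concealed allocation by ICU, with the smallest units merged and ICU replacing gender as the stratifier, or minimise on ICU and gender together. Full cross-stratification is unsuitable: 7 × 2 = 14 strata would hold about 168/14 = 12 patients each, over three arms.
- **Analysis.** Pre-specify ICU as a factor in the pepsin comparison, by two-way ANOVA or a linear model, on log pepsin if the distribution is skewed. If a rank test is preferred, use the stratified rank test (van Elteren) in place of Mann-Whitney U.
- **If allocation has begun.** Make the analysis change alone, and fix it before outcomes are seen.

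A table of pepsin by arm within each ICU is not needed: 3 × 7 = 21 cells would hold about 168/21 = 8 patients each, too few to interpret.

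**Cost.** A revised allocation list, one more recorded variable and one more term in the analysis. The downside is a few incomplete blocks in small units and about 5 to 6 of the 168 − 3 = 165 residual degrees of freedom.

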### Study Protocol

#### Aim

The aim of this randomized controlled trial was to determine the effect of three different ETT cuff pressure controls used in ICU patients receiving mechanical ventilator support using an ETT on preventing microaspiration of gastric content and on VAP development within 48 hours after intubation.

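### No outcome or pepsin time point is named primary, and every p value below 0.05 counts as significant, so the chance of a false claim exceeds 5%

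*Combined protocol and SAP*

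**What the plan says.** All references are to the combined protocol and SAP.

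- **Aim.** Three methods of cuff-pressure control are to be judged "on preventing microaspiration of gastric content and on VAP development within 48 hours after intubation". These are two outcomes, and neither is ranked above the other.
- **Study design.** The trial "compares finger palpation of the pilot balloon, intermittent and continuous ETT cuff pressure used to prevent microaspiration of gastric content for ICU patients". VAP is not mentioned here.
- **Study population.** The sample size uses d = 0.5, alpha 0.05 and power 0.80. It gives 51 per group, raised to 56 for losses. The variable to which d applies is not stated.
- **Intervention and Assessment.** Pepsin is measured three times. "The first deep tracheal secretion sample to be used to determine pepsin I level will be taken four hours after intubation". Pepsin II covers hours 5 to 24. Pepsin III starts at hour 25 and is "collected by the 48th hour of the intubation or the patient is discharged or exitus". The section describes no assessment of VAP.
- **Statistical analysis.** On the choice of test: "Kolmogorov-Smirnov Test will be used to check the appropriateness of data to normal distribution". Where that check is passed, a two-group and a three-group test are named in one breath: "Independent two-sample t-test, one-way analysis of variance will be used for the relationships between the variables that fit the normal distribution". Where it is failed, the plan offers a two-group rank test and nothing for three arms: "the Mann Whitney U test will be used for the variables that do not fit the normal distribution". Categorical data get Pearson chi-square or Fisher exact tests. The section ends with the decision rule: "All p values lower than 0.05 will be taken as significant in all results".

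No section contains a primary or secondary label, a test order, a gate, a post hoc procedure or an adjustment of alpha.

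**The concern.** The closing sentence goes further than silence on multiplicity, because it gives every result the same 5% threshold. Followed as written, it lets a significant result on any pepsin sample, or on VAP, support the claim that the cuff-control methods differ. The result to be emphasised could be chosen after the data are seen. The trial's central conclusion would then carry a false-positive risk above the nominal 5%, by an amount that depends on how many tests are run.

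That number is itself open. For normal variables the plan lists a two-group and a three-group test together, without saying how they relate. For non-normal variables it names only a two-group test, although there are three arms.

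**Working it through.** **1. The plan's own figure.** The plan states no overall error rate, only 0.05 per test. Its sample size matters here only for the cost of the fix. At d = 0.5 and 51 per group, a two-sample t-test has power 0.706 two-sided and 0.806 one-sided. Whether 51 per group delivers the stated 0.80 is a separate question.

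**2. Inputs.**
- From the documents: three arms, 56 per arm, three pepsin samples, VAP, and 0.05 for each test.
- Assumed, because the documents do not give them: within-patient pepsin correlation ρ from 0.9 to 0, VAP rate 20%, and VAP independent of pepsin.

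**3. Independent tests (ρ = 0).** With k independent tests, the chance of at least one false claim is 1 − (1 − 0.05)^k.
- k = 2 (pepsin II and III): 1 − 0.95² = 0.0975
- k = 3 (pepsin I to III): 1 − 0.95³ = 0.143
- k = 4 (pepsin I to III and VAP): 1 − 0.95⁴ = 0.185

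**4. Correlated tests.** Simulation with no true difference, 40,000 trials per setting, 56 per arm, two-sided tests at 0.05. The Monte Carlo standard error near 0.10 is √(0.10 × 0.90 / 40,000) = 0.0015.

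| Tests counted | ρ = 0 | 0.5 | 0.7 | 0.9 |
|---|---|---|---|---|
| ANOVA on pepsin II, III | 0.095 | 0.092 | 0.085 | 0.071 |
| ANOVA on pepsin I–III | 0.140 | 0.127 | 0.110 | 0.084 |
| ANOVA on pepsin II, III; 3×2 test on VAP | 0.142 | 0.135 | 0.131 | 0.116 |
| ANOVA on pepsin I–III; 3×2 test on VAP | 0.183 | 0.169 | 0.155 | 0.129 |
| *If Mann-Whitney is run on all three pairs:* | | | | |
| one pepsin sample | 0.120 | 0.122 | 0.124 | 0.120 |
| two samples | 0.227 | 0.216 | 0.202 | 0.168 |
| three samples | 0.320 | 0.289 | 0.257 | 0.199 |
| three samples; 3×2 test on VAP | 0.355 | 0.323 | 0.294 | 0.238 |

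Hand check of the last row at ρ = 0: 1 − (1 − 0.12)³ × 0.95 = 1 − 0.681 × 0.95 = 0.353.

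**5. Sensitivity.**
- Kruskal-Wallis in place of ANOVA agrees within 0.003, and 51 per arm agrees within 0.01.
- VAP rates from 5% to 50% move the figures by at most about 0.01.
- Letting VAP depend on pepsin (latent correlation up to 0.6) lowers them by at most about 0.013.
- The last row is not a ceiling. Testing VAP by pair as well gives 0.30 to 0.41.

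**6. Does a gate restore 5%?** Suppose one outcome is tested across three groups at 0.05, and the pairs are tested at 0.05 only if that test is significant. If no arm differs, a false pair claim needs a false overall result first. If one arm differs, only one pair is truly equal, and it is tested at 0.05.

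Simulated rates of any false pair claim, with the Kolmogorov-Smirnov choice of test included:
- normal data: 0.049
- lognormal with log SD 0.25, 0.5 and 1.0: 0.053, 0.050 and 0.049
- t with 5 df: 0.049
- without the gate: 0.122 to 0.128

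With one arm truly different (d from 0.3 to 2), the equal pair is falsely claimed in 0.041 to 0.050 of trials. For VAP, with Fisher exact when expected counts are small, the rate is 0.002 to 0.052 for VAP rates of 2% to 50%.

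**The case against.** The strongest reply is that the documents already point to a lead outcome. The Study design section mentions only microaspiration. The sample size uses d = 0.5, which is conventionally a standardised difference in means and so implies a continuous outcome. The assessment section describes sampling for pepsin alone. Pepsin I, taken at four hours, might be seen as close to a baseline. The 0.05 sentence can also be read as a nominal threshold rather than a rule that any one significant result proves efficacy.

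Much of this stands. Pepsin is the natural lead, and readings that include VAP are the less natural ones. But setting aside both pepsin I and VAP still leaves two candidate samples, no stated choice between them, and a false-claim chance of 0.07 to 0.10. Reading the threshold as merely nominal does not say which result would decide the trial.

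A reader might also infer that the plan prescribes pairwise testing throughout and so carries a risk of about 0.36. The documents do not support that. Running Mann-Whitney on each pair is an inference from its being the only test named for non-normal data, and ANOVA is named for normal data. The 0.36 end also needs zero correlation between repeated samples from the same patient. At the more plausible 0.5 to 0.9, that scenario gives about 0.24 to 0.32.

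**Conclusion.** The concern holds. The plan does not say which outcome and time point decide the trial, and its decision rule gives every result an unadjusted 5% threshold.

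On the least inferential reading (three-group tests of pepsin II and III), the chance of a false claim is 1.4 to 2 times nominal: 0.07/0.05 = 1.4 and 0.10/0.05 = 2. Counting all three samples and VAP, it is 0.13 to 0.19. Ungated pairwise testing would raise it to about 0.12 for a single sample and about 0.24 to 0.36 for three samples plus VAP, but only if that inferred reading is what the investigators intend.

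The missing primary outcome and the unadjusted rule are facts of the text. The sizes rest on the assumed pepsin correlation and, where VAP is counted, on its assumed rate and independence from pepsin.

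A reader might infer that only a single confirmatory test can hold 5%. That is not so: gated pairs, fixed-order testing and split alpha also do.

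**What to change.** Before results are seen, name one primary outcome and time point. One pepsin sample fits the design, sample-size and assessment sections best, but the choice is the investigators'. Then state that:

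- The primary outcome is compared across the three groups at two-sided 0.05. For pepsin, use one-way ANOVA, or Kruskal-Wallis if the data are not normal by a rule fixed in advance (the check above used Kolmogorov-Smirnov p < 0.05 in any group).
- The three pairs are each tested at 0.05 only if the overall test is significant, with t-tests after ANOVA or Mann-Whitney after Kruskal-Wallis.
- The sentence on significance applies to the primary outcome only, and other p values are descriptive.

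This holds the false-claim rate at about 0.05. It is one acceptable scheme among several. If more than one outcome must be confirmatory, use a fixed order or split alpha.

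Two choices need additions:
- **Pepsin III:** state how collections cut short by discharge or death are analysed.
- **VAP:** state how and when it is assessed, use a 3×2 chi-square or Fisher exact test, and restate the power, because the d = 0.5 calculation would not apply.

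**Cost.** A few sentences, one added test (Kruskal-Wallis) and some pairwise power. At d = 0.5 and 51 per group, two-sided t-test power for a pair falls from about 0.71 to 0.65 if one arm differs, or 0.59 if the third arm lies midway. With all 56 per group analysed, it falls from 0.75 to about 0.69 or 0.63. At 51 per group, rank-test power falls from 0.68 to 0.62 or 0.56.
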